7.5 Criteria for withdrawal / discontinuation of participants

The criteria for withdrawal of participants are either the request of participants to be withdrawn from the study or SAE, related to exercise of IMPs or other medication applied during general anesthesia, including signs of cardiac arrhythmia or other evidence of drug incompatibility resulting in hemodynamic instability.

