8. STUDY INTERVENTION

8.1 General information

Patients will randomly be allocated either to the “lidocaine group“, or the “placebo group”. The only difference between both groups will be the implementation of a systemic lidocaine infusion during perioperative phase. All over management and techniques of anesthesia will be handled as described in the current “Standard Anaesthesie KSSG”. It includes detailed description of anesthesiological procedures for specific surgical interventions. Patients listed for bariatric surgery receive detailed information about anesthesiological techniques, course and management of adverse effects due to medical side effects or surgical complications during the preoperative anesthesiological consultation. On the day of surgery, the patient will receive premedication of 1 mg paracetamol p.o. one hour before planned intervention. Apart from the study intervention, standard anesthetic technique and pain management (related to practice of the anesthesiological standard of the Kantonsspital St. Gallen will be used in all the patients at the discretion of the attending anesthesiologist (use of alternative aminoamid local anesthetics, as additional analgesic will be prohibited during treatment and hospitalization of patients included to the study). After securing intravenous line, monitoring will be installed. Baseline parameters will be observed and recorded in the ACPDMS. Fentanyl ($\approx 0.002 \dots 0.003$ mg/kg) will be given intravenously two minutes before the induction of anesthesia in both groups. Airway management in patients with a mean BMI > 35 kg/cm² is performed by fiberoptic nasal intubation in awake condition. Nasal drops (0.25 ml cocainehydrochloride 10%) will be applied and transcrucial application of 2 ml lidocaine 1% for anesthesia of the upper airway will be performed before advancing the fiberscope into the trachea. As soon as vocal cords are crossed, induction of general anesthesia will be induced with etomidate 0.2 mg/kg bodyweight. Thereafter the nasotracheal tube is placed. Anesthesia will be maintained by target controlled infusion of propofol 1% and remifentanyl 40 μ g/ml according to institutional standards in all patients. Neuromuscular blockade will be achieved by bolus followed by continuous administration of rocuronium as clinically necessary.

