8.5 Dose modifications

If SAE will be recognized, infusion of investigational product will be stopped and arrangements conducted to treat potential adverse effects and ensure patients` safety. The Principal Investigator will be informed about the incident within 24 hours.

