9.3 Assessments of safety outcomes

Vital parameters (blood pressure, pulse rate, oxygen saturation) will be recorded digitally by the electronic acute care patient data management system (ACPDMS) during the peri- and postoperative phase and according to institutional standards.. During the entire surgical and anaesthetic procedure and in the PACU trained personnel will be present monitoring vital parameters and the patient clinical status. Every deviation to normal course will be treated and recorded according clinical standards of the institution. SAE related to the administration of the IMP will cause an immediate cessation of the drug administration and will be reported to the Sponsor Investigator not later than 24 hours after the event.

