9.4 Procedures at each visit

Each patient will be visited after surgical treatment and transfer to PACU/ICU by a study nurse or the Study Investigator. The VAS/NRS score (registration of any development of VAS/NRS score > 3) will be assessed by trained nurse practitioners in the PACU/ICU in hourly measurements during the first four hours after completion of surgery, respectively until discharge to the surgical ward. Thereafter, VAS/NRS score will be assessed by a patient questionnaire for self-evaluation and in addition by trained nurse practitioners during their daily round (10am and 2pm respectively ± 30 minutes) during the first four hours and during 48 hours after completion of surgery. VAS/NRS scores and vital parameters will be recorded. Incidental questions about upcoming study process will be answered. Infusion of the investigational product will be stopped four hours after the end of surgery (or before the transfer of the patient from the PACU to the surgical ward, whichever occurs first). Pain evaluation will take place every eight hours by recording the maximum VAS/NRS score experienced within this period. Recording of VAS/NRS scores will be stopped at 2pm respectively ± 30 minutes on second postoperative day. Completion of study investigation will be finalized by collecting the study documents at study nurses final visit on second postoperative day at 2pm respectively ± 30 minutes.

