10.4 Planned Analyses

Following populations will be analyzed

- Interventional group (patients receiving lidocaine 1% I.V. in addition to general anesthesia)
- Control group (patients receiving saline 0.9% as placebo I.V. in addition to general anesthesia)
- whole population (evaluation of secondary endpoints)

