10.8 Handling of missing data and drop-outs

Missing postoperative VAS/NRS scores, required for primary and secondary endpoints, will be handled as interpolation values, calculating an average score between last recorded scores before and after the missing value. Missing data for secondary endpoint PONV or time to first defecation will be handled as no occurrence of PONV (PONV 0) or no defecation yet. In case of drop-out, data collected till patients drop out will be neglected and not taken into account of statistical consideration of the study.

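### Section 10.8 discards all of a drop-out's data and 7.5 makes a related SAE grounds for withdrawal, so on the natural reading a randomized patient can leave the primary analysis with the endpoint already met

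*Combined protocol and SAP*

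**What the plan says.** - **Timing.** Randomization follows consent at the preoperative consultation, usually two to three weeks before admission (6.3, 7.3, 7.4). Any SAE from the study drug or the anesthetic is therefore a post-randomization event.
- **Withdrawal.** Section 7.5 names two grounds: "request of participants to be withdrawn from the study or SAE, related to exercise of IMPs or other medication applied during general anesthesia".
- **Action on an SAE.** Section 8.5 says "If SAE will be recognized, infusion of investigational product will be stopped", and 9.3 says "SAE related to the administration of the IMP will cause an immediate cessation of the drug administration". Neither says whether the patient stays in the study.
- **Drop-outs.** Under 10.8, "data collected till patients drop out will be neglected and not taken into account of statistical consideration of the study". The term is not defined there or elsewhere.
- **Missing scores.** Section 10.8 interpolates by "calculating an average score between last recorded scores before and after the missing value".
- **Populations.** Section 10.4 lists the two arms, described by what patients receive, and a "whole population (evaluation of secondary endpoints"). It names no all-randomized set for the primary outcome.
- **Scoring.** Under 9.4 the pain score "will be assessed by trained nurse practitioners in the PACU/ICU in hourly measurements during the first four hours after completion of surgery", so a move to the ICU does not by itself end pain assessment.

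**The concern.** Stopping the study drug and leaving the analysis are different things, and the plan does not keep them apart. The primary outcome is met by a single hourly score above 3. Suppose a patient exceeds 3 at the first measurement and has a related SAE before the second. The outcome is then known, yet 7.5 and 10.8 read together delete that patient. A patient who withdraws on request after such a score reaches the same rule.

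Removing patients for something that happens after randomization, and that treatment may have caused, means the groups compared may no longer be the groups randomized. If removal is related both to arm and to pain, the difference in proportions is biased.

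**Working it through.** **1. The plan's own figure.** Inputs from 10.2 and 10.3: 65% versus 35%, two-sided 0.05, 90% power, 10% drop-out.
- Uncorrected: n = [1.96·√(2·0.5·0.5) + 1.2816·√(0.65·0.35 + 0.35·0.65)]² / 0.30² = 56.3, so 57 per group.
- Continuity-corrected: (56.3/4)·[1 + √(1 + 4/(56.3·0.30))]² = 62.8, so 63 per group, as stated.
- Drop-out: 63/0.9 = 70 per group, 140 in total. The plan thus allows for 14 drop-outs, 7 per arm if balanced.

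The sample size is sound. The question is only who is counted.

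**2. Does any text rescue the patient?** Sections 8.5 and 9.3 stop the infusion only. Section 10.4 names no all-randomized set. Sections 11.2 and 11.8 preserve safety follow-up, not pain scores in the analysis. Interpolation needs a score on both sides of the gap, so it cannot serve a patient whose scores have ended. Nothing found retains the scores.

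**3. Shift in the lidocaine rate.** The exclusion counts k are assumptions, because the documents give no SAE rate. Extreme case: k excluded from lidocaine only, 70 per arm, planned lidocaine events 0.35·70 = 24.5.
- k = 1: 23.5/69 = 34.1% if that patient had pain; 24.5/69 = 35.5% if not.
- k = 3: 21.5/67 = 32.1% if all had pain; 24.5/67 = 36.6% if none had.

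The shift is at most −2.9 to +1.6 points on a planned 30-point difference.

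**4. False-positive chance with no true effect** (65% in both arms). Each full arm is Bin(70, 0.65). The stated patients are then removed, and an uncorrected χ² test at two-sided 0.05 is evaluated by exact enumeration.

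| Excluded, lidocaine v placebo | Falsely favours lidocaine | Falsely against lidocaine |
|---|---|---|
| none | 2.49% | 2.49% |
| 1 v 0, had pain | 3.11% | 2.23% |
| 1 v 0, no pain | 2.06% | 3.45% |
| 3 v 0, all had pain | 4.23% | 1.68% |
| 3 v 0, none had pain | 1.26% | 6.16% |
| 3 v 3, all had pain | 2.64% | 2.64% |
| 3 v 3, none had pain | 3.09% | 3.09% |
| 3 v 0, unrelated to pain | 2.73% | 2.59% |

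**5. Towards the drop-out allowance.** If 7 lidocaine patients, all with pain, and no placebo patients are lost, the lidocaine rate becomes (45.5 − 7)/63 = 61.1%, a false difference of −3.9 points. Treating that arm as Bin(63, 0.611) gives a 6.3% chance of falsely favouring lidocaine. The same approximation gives 4.13% for 3 v 0, against 4.23% above.

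**6. Power at 65% versus 35%.** It is 95.3% with no exclusion. With 3 lidocaine-only exclusions it is 97.5% if all had pain and 92.0% if none had. With 7 excluded per arm, unrelated to pain, it is 93.7%.

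**The case against.** **The link is inferred.** No sentence says that a 7.5 withdrawal is a 10.8 drop-out. The heading of 7.5 covers discontinuation as well, and 8.5 and 9.3 only stop the drug. A reading in which the SAE ends the infusion but not participation is available. This stands as a caveat. It does not remove the point: 7.5 speaks of withdrawing participants, requests to leave reach the same rule, and if the sponsor meant otherwise the plan still has to say so.

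**The effect is small.** This stands. One exclusion barely moves the error rate. The larger figures need several exclusions, all in one arm and all with the same pain outcome.

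**A reader might infer that the rule favours lidocaine**, because infusion toxicity can arise only in that arm. The documents do not support this. The trigger in 7.5 includes other anesthetic medication. Section 8.1 describes airway anesthesia without distinction by arm ("application of 2 ml lidocaine 1% for anesthesia of the upper airway will be performed"). Treating staff are blinded (6.1, 6.4), so a placebo patient's event can also be attributed to the study drug. The meta-analysis described in 3.2 found no evidence of higher risk of intoxication, arrhythmia or death, and a study cited in 3.5 found adverse effects comparable with placebo. Whether an excluded patient had pain is also unknown, and the table shows that the sign depends on it.

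**How often the trigger fires cannot be read from the plan.** Section 11.6 counts drowsiness or confusion due to the study drug as severe, and hence as an SAE, which widens it. Section 11.7 keeps outcome events out of SAE reporting unless they are exceptional, which narrows it.

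**A reader might also infer that safety data are lost.** They are not: 11.2 and 11.8 continue follow-up of patients with ongoing SAEs.

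**Conclusion.** The point holds as a gap in the analysis rule, at the level of something the sponsor should correct. What is certain is that 10.8 discards recorded scores of any drop-out and that no all-randomized set is named for the primary outcome. What is inferred, though natural, is that a related SAE under 7.5 makes the patient a drop-out.

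The bias is of unknown direction and probably small. With 1 to 3 lidocaine-only exclusions, the chance of falsely favouring lidocaine lies between 1.3% and 4.2%, against 2.5% with none. The planned difference moves by less than 3 points, and power stays at 92% or more. These figures rest on assumed counts. Exclusions as large as the drop-out allowance would matter more if unbalanced and related to pain, but the documents give no ground to expect that. The case for acting is that the exclusion is unnecessary, since scoring can continue, and cheap to remove.

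**What to change.** **Section 7.5.** State that an SAE stops the study drug only, and that the scheduled pain assessments continue unless the patient withdraws consent.

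**Section 10.8.** Replace the sentence on drop-out data with the following:
- An infusion stop is not a drop-out.
- Scores recorded before withdrawal are kept unless consent to their use is withdrawn.
- Patients are analysed in their randomized group.
- Any recorded score above 3 in the first four hours counts as an event.

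Keep interpolation for isolated gaps. For withdrawn patients with no score above 3 and no later score, report two sensitivity analyses, counting them once as events and once as non-events.

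A blanket rule that missing means event in the main analysis is not advised. Section 9.4 can be read as ending hourly scoring at discharge to the ward, while 9.2 mentions scoring there too, so a comfortable patient transferred early could be labelled a failure. It can also be costly. With 7 unscored on lidocaine only (an assumption), power falls to 81.6%, against 94.3% if they are excluded and unrelated to pain.

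**Cost.** Amendment wording, with no new visits or measurements. Scores after an early stop reflect a shortened infusion and may slightly dilute the effect.

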8. STUDY INTERVENTION

8.1 General information

Patients will randomly be allocated either to the “lidocaine group“, or the “placebo group”. The only difference between both groups will be the implementation of a systemic lidocaine infusion during perioperative phase. All over management and techniques of anesthesia will be handled as described in the current “Standard Anaesthesie KSSG”. It includes detailed description of anesthesiological procedures for specific surgical interventions. Patients listed for bariatric surgery receive detailed information about anesthesiological techniques, course and management of adverse effects due to medical side effects or surgical complications during the preoperative anesthesiological consultation. On the day of surgery, the patient will receive premedication of 1 mg paracetamol p.o. one hour before planned intervention. Apart from the study intervention, standard anesthetic technique and pain management (related to practice of the anesthesiological standard of the Kantonsspital St. Gallen will be used in all the patients at the discretion of the attending anesthesiologist (use of alternative aminoamid local anesthetics, as additional analgesic will be prohibited during treatment and hospitalization of patients included to the study). After securing intravenous line, monitoring will be installed. Baseline parameters will be observed and recorded in the ACPDMS. Fentanyl ($\approx 0.002 \dots 0.003$ mg/kg) will be given intravenously two minutes before the induction of anesthesia in both groups. Airway management in patients with a mean BMI > 35 kg/cm² is performed by fiberoptic nasal intubation in awake condition. Nasal drops (0.25 ml cocainehydrochloride 10%) will be applied and transcrucial application of 2 ml lidocaine 1% for anesthesia of the upper airway will be performed before advancing the fiberscope into the trachea. As soon as vocal cords are crossed, induction of general anesthesia will be induced with etomidate 0.2 mg/kg bodyweight. Thereafter the nasotracheal tube is placed. Anesthesia will be maintained by target controlled infusion of propofol 1% and remifentanyl 40 μ g/ml according to institutional standards in all patients. Neuromuscular blockade will be achieved by bolus followed by continuous administration of rocuronium as clinically necessary.

Study intervention: Patients in the “lidocaine group” will receive 1.5 mg/kg lean body mass of lidocaine 1% bolus intravenously after induction of general anesthesia (as soon

as general anesthesia's steady state is accomplished), followed by a continuous infusion of lidocaine 1% with 1.5 mg/kg lean body mass/h during surgery and continued for four hours after completion of surgery or until the discharge from the PACU, whatever comes first. Patients in "placebo group" will receive 0.15 ml/kg lean body mass of saline 0.9% bolus I.V. after induction of general anesthesia (as soon as general anesthesia's steady state is accomplished), followed by continuous infusion of NaCl 0.9% I.V. with 0.15 ml/kg lean body mass/h during surgery and continued for four hours after completion of surgery or until the discharge from the PACU, whatever comes first. Maintenance of general anesthesia and optional application of additional opiates for pain treatment (fentanyl 0.1 - 0.2 mg as an intravenous bolus) during surgery is under discretion of the attending anesthesiologist and is related to the practice of standardized pain management and will be equal in both groups. Similarly, postoperative treatment in the PACU and further on the surgical ward, are under discretion of the clinically responsible physicians, relating to current practice of standardized pain management at the Kantonsspital St. Gallen (Schmerzkarte KSSG).

A detailed graphical version of study sequences is provided in german as follows:

Periode	Ort	Intervention	Details
Anmeldung	Studien- koordination	Screening	Ein- / Ausschlusskriterien evaluieren
		erfüllt	
PAS Termin	PAS	Informed consent	Aufklärung und Einwilligung durch Patienten
		erfüllt	
PAS Termin	PAS	Randomisierung	Zuteilung zur Gruppe Lidocain oder Placebo
OP Datum	OPS 03	Intervention COALAS	- IMP Bolus ab AN steady state - anschliessend Beginn IMP Perfusor - Datenerfassung ACPDMS (Medis, Vitalparameter) - AE, SAE, ADR erfassen
		Transfer	
POD 0	PACU	VAS Monitoring VAS Evaluationsbogen	- IMP Perfusor bis 4 Std. ab "OP-Ende" od. Transfer auf Abteilung - VAS 1.,2.,3.,4. Std. - Datenerfassung ACPDMS (Medis, Vitalparameter) - Prim./Sek. Variablen im CRF erfassen - AE, SAE, ADR erfassen
		Transfer	
POD 0	ABTEILUNG	VAS Monitoring 2pm, 10pm Studiensite 10am, 2pm	- Erinnerung des Pat. durch Pflege- Studienpersonal - Prim./Sek. Variablen im CRF erfassen - AE, SAE, ADR erfassen
POD 1	ABTEILUNG	VAS Monitoring 6am, 2pm, 10pm Studiensite 10am, 2pm	- Erinnerung des Pat. durch Pflege- Studienpersonal - Prim./Sek. Variablen im CRF erfassen - AE, SAE, ADR erfassen
POD 2	ABTEILUNG	VAS Monitoring 6am, 2pm Studiensite 10am, 2pm (Safety follow-up)	- Erinnerung des Pat. durch Pflege- Studienpersonal - Prim./Sek. Variablen im CRF erfassen - AE, SAE, ADR erfassen
POD X	Studien- koordination	Safety follow-up	- telefonisch / ambulant - AE, SAE, ADR erfassen

table 2: study sequence describing process and daily course, POD X will be postoperative day seven or day of patients discharge

8.2 Identity of Investigational Products

Lidocaine hydrochloride 1% by Streuli Pharma is a sterile, nonpyrogenic solution of lidocaine hydrochloride in water for injection for parenteral administration. Dosage of 1.5 mg/kg LBM will be calculated individually. Injection of 1.5 mg/kg LBM bolus will be performed as soon as steady state concentration of general anesthesia is accomplished. Steady infusion of lidocaine 1.5 mg/kg/h LBM will be initiated with the beginning of surgical procedures and estimated duration of infusion will be four hours after completion of surgery (expecting an average of two hours of surgery and four hours monitorization in PACU till transfer to surgical ward). Dosage and average duration of application represents references in current literature.

Additional IMP in placebo group will contain saline (Natrii chloridum 0.9%), which will be provided by Grosse Apotheke Dr. G. Bichsel AG. Dosage of 0.15 ml/kg LBM will be calculated individually and represents an equivalent amount (in ml) of IMP used in the interventional group. Injection of 0.15 ml/kg LBM bolus will be performed as soon as steady state concentration of general anesthesia is accomplished. Steady infusion of NaCl 0.9% 0.15 ml/kg/h LBM will be initiated with the beginning of surgical procedures and estimated duration of infusion will be four hours after completion of surgery (expecting an average of two hours of surgery and four hours monitorization in PACU till transfer to surgical ward).

8.3 Packaging, Labelling and Supply

Lidocaini hydrochloridum (Lidocaine Streuli®) will be provided by Streuli Pharma AG, Switzerland (Swissmedic registration number: 300 16).

Saline (Natrii chloridum 0.9%) will be provided by Grosse Apotheke Dr. G. Bichsel AG, Switzerland (Swissmedic registration number: 298 00).

Syringes and ampulles containing the IMPs (Lidocaine 1% or Saline 0.9%) used during the study will be labelled notably. Distinct labels for ampulles and syringes include information about IMPs`origin, charge number, dedicated patient`s ID, fabrication and expiration date (see appendix for a detailed graph of IMP labels). Blinded personel (practitioner, nurses, surgeon, etc.) will not be able to distinguish between the containing IMPs

due to identical appearance and labeling. An additional code to reproduce its origin will also be visible. No special storage conditions are needed for the IMPs. Prepackaging, assembly, blinding procedure and labeling of syringes will be organized by the pharmacy of the Kantonsspital St. Gallen. Personnel related to the peri- and postoperative course (anesthesiology, surgery, PACU, follow-up on surgical ward) will be blinded by the above-mentioned methods. Study specific labeled syringes will be fabricated individually for each patient and on request one to two days before surgery and will be delivered to the OR on the day of surgery and preparation of syringes (connection to syringe pump) will be conducted by anesthesiological employees.

To ensure product safety for human consumption/application, Good Manufacturing Practice will be conducted.

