6.4 Blinding procedures

All patients will be blinded to their randomization. Attending physician and other personnel responsible for patients` care (peri- and postoperative) will be blinded. Syringes used for application of interventional drugs will be blinded, labelled as “interventional drug”. Unblinding, in case of SAE or suspected unexpected serious adverse reactions and to guarantee patients safety, will be executed by the Principal Investigator.

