8.9 IMPs / Medical Device Accountability

IMP Lidocaine will be provided by Streuli Pharma AG, Switzerland and IMP saline will be provided by Grosse Apotheke Dr. G. Bichsel AG, Switzerland. Storage and distribution will be organized by the pharmacy of the Kantonsspital St. Gallen, as well as prepackaging, assembly, blinding procedure and labeling. Adequate records about maintenance, shipment to the site, return or disposal of remaining or expired IMPs, physical location, dates of receipt, expiry, use and return, stock numbers and quantities received, used or destroyed will be recorded, referring to GMP. The pharmacy of the Kantonsspital St. Gallen is certified with the cantonal approval of manufacturing (kantonale Herstellungsbewilligung).

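### Section 8.3 puts product origin and charge number on the syringe label while the arms have different suppliers, and the text does not rule out that blinded staff can read the arm from it

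*Combined protocol and SAP*

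**What the plan says.** On label content, section 8.3 has "Distinct labels for ampulles and syringes include information about IMPs`origin, charge number", followed by patient ID and the fabrication and expiry dates. It then adds "An additional code to reproduce its origin will also be visible". Between these two sentences it promises that "Blinded personel (practitioner, nurses, surgeon, etc.) will not be able to distinguish between the containing IMPs", and gives identical appearance and labelling as the reason. It refers to an appendix for a picture of the labels.

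On blinding, section 6.4 has "Syringes used for application of interventional drugs will be blinded", and the same sentence goes on to say that they are labelled as the interventional drug. Sections 6.1 and 6.2 also rely on equal appearance and packing.

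On supply, section 8.9 has "IMP Lidocaine will be provided by Streuli Pharma AG, Switzerland and IMP saline will be provided by" a different company. Sections 8.2 and 8.3 name the same two suppliers. The hospital pharmacy prepackages, assembles, blinds and labels, and makes the syringes up for each patient one to two days before surgery (8.3).

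**The concern.** One section lists label fields that could differ by arm and also says that the labels are identical. If the fields refer to the source product, a nurse or anesthetist who reads the syringe knows the allocation.

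The outcome is open to that knowledge. The primary endpoint is any VAS/NRS score above 3 at hourly readings in the first four hours after surgery, recorded by PACU or ward nurses (5.1, 9.2). Opioid boluses during surgery and analgesia afterwards are discretionary within the hospital's standards (8.1). Knowing the arm could affect how pain is asked about and recorded, and how readily it is treated before the next reading. Randomization and blinding are the only protections against bias that 6.2 names.

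**Working it through.** **1. The statements side by side.**

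| Section | What it implies for the label |
|---|---|
| 8.3, label list | Origin, charge number, patient ID, fabrication and expiry dates |
| 8.3, later sentence | A visible origin code in addition |
| 8.3, between the two | Identical labelling; staff cannot tell the products apart |
| 6.4 | Neutral label |
| 8.2, 8.3, 8.9 | One supplier for lidocaine, another for saline |

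**2. Two readings of origin and charge number.**

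- *Source product.* Origin is the supplier and charge number is the supplier's batch. A supplier name differs by arm, so the labels cannot be identical. A supplier batch would also belong to one arm, and patients supplied from the same batch would share it.
- *Pharmacy preparation.* Origin is the hospital pharmacy and charge number is its preparation number for that patient. Nothing on the label then depends on the arm, and 8.3 and 6.4 agree.

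The text does not choose between them. Section 8.3 opens by naming the two suppliers, which points to the first. Per-patient fabrication by the pharmacy points to the second.

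**3. Exposure.** Anesthesia staff connect the labelled syringes to the pump (8.3). The infusion runs for up to four hours after surgery or until PACU discharge, whichever comes first (8.1). The syringe can therefore be at the bedside while nurses record the hourly scores that make up the primary endpoint (9.2).

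**4. Illustration of size.** The documents give no figure for a bias from unblinding, so the shifts below are assumptions.

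The planned sample size comes first, because it supplies n. With 65% v 35%, two-sided 0.05 and 90% power (10.3):

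n₀ = [1.960·√(2·0.5·0.5) + 1.282·√(0.65·0.35 + 0.35·0.65)]² / 0.30² = 56.3, that is 57 per group.

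With continuity correction, n = (n₀/4)·[1 + √(1 + 4/(n₀·0.30))]² = 62.8, that is 63 per group. This matches the plan. Then 63/0.9 = 70 per group, 140 in total.

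Now suppose that lidocaine has no effect (65% in both arms) and that unblinded recording lowers the lidocaine rate to p. The chance of p-value < 0.05 is

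Σₓ Σᵧ Bin(x; 63, 0.65) · Bin(y; 63, p) · 1{χ²(x, y) > 3.841}.

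| Recorded rates | Assumed shift | Uncorrected χ² | Continuity-corrected χ² |
|---|---|---|---|
| 65% v 65% | 0 | 5.1% | 3.2% |
| 65% v 60% | 5 points | 9.4% | 6.5% |
| 65% v 55% | 10 points | 22.3% | 17.2% |

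A normal approximation to the uncorrected test gives 5.0%, 8.9% and 20.7%, close to the exact values. Both columns are shown because 10.5 does not say which version of the test is meant, while the sample size reproduces only with the correction.

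**The case against.** The strongest defence is the pharmacy reading. The charge number is listed beside patient ID and fabrication date, for a product made individually one to two days before surgery. These can naturally be the fields of a pharmacy preparation label. Four places (6.1, 6.2, 6.4 and 8.3) state that labels or packaging do not give the arm away, and the label picture that would decide the matter was not available. All of this stands, and it is why the point stops short of a demonstrated fault.

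Stronger inferences are tempting but not supported:

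- *The two statements in 8.3 cannot both be true.* They can, if the fields describe the pharmacy's own preparation.
- *Patients in one arm share a batch number, so one unblinding exposes others.* This holds only for a supplier batch. A per-patient preparation number is shared by nobody.
- *The word distinct in 8.3 means labels that differ by arm.* It can equally mean separate labels for ampoules and for syringes.
- *The visible tracing code must go.* A code unique to each patient that only the pharmacy can decode does not reveal the arm. Some such link is needed for tracing.

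It is also fair to say that the assumed shifts are net shifts across a whole arm and give no evidence that a leak would occur. What the defence does not supply is any sentence that excludes the source-product reading.

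**Conclusion.** The label specification in 8.3 is open to a reading that defeats the blinding promised there and in 6.4, and nothing in the available text closes it. The risk matters because the labelled syringe can be in view where a subjective primary endpoint is recorded. Whether allocation would in fact be visible is undetermined.

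The numerical size is conditional on assumption. A net recording shift of 5 points would roughly double the false-positive rate, and one of 10 points would raise it to about 17% to 22%, depending on the continuity correction. The correction is worth making before syringes are labelled.

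**What to change.** In 8.3, replace the origin and charge-number fields with a statement that no supplier name, supplier batch number or arm-specific code is visible to blinded staff. The label would then show:

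- the neutral study label from 6.4;
- the patient ID or a per-patient kit or preparation number;
- fabrication and expiry dates;
- if wanted, a tracing code that is unique per patient and decodable only by the pharmacy.

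Record supplier and source batch against the patient's number in the pharmacy accountability log. Section 8.9 already provides for stock numbers, quantities and dates of use, so this adds one explicit item. Check the label appendix against the revised text. If the pharmacy's own origin and preparation number were meant all along, say so in 8.3.

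The cost is a wording change and, if needed, a new label template. The downside is that batch tracing runs through the pharmacy log and no longer through the syringe itself. The documents place preparation under GMP but do not say which fields a label must carry, so the pharmacy should confirm that the reduced label is acceptable. Emergency unblinding is unaffected, because 6.5 uses a separate envelope.
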